## F2. Psychological risks to participants

In all study arms there is a risk of potential discomfort in talking about weight-related behaviors.

**Protection against risk.** Participants will be informed that sharing of all information is voluntary both during data collection and counseling sessions. They will be encouraged to share concerns with weight-related issues during the sessions only to the extent that they feel comfortable. Participants who have suspected mental health diagnoses that may interfere with ability to adhere to program recommendations will be referred to the treating PCP. PCPs will also be alerted if participants score  $\geq 20$  on the PHQ-9 and/or endorse the suicide ideation question. In addition, patients will be advised to follow-up with their PCP or mental health provider if they score  $\geq 15$ , and if they also endorse the suicide ideation question, the PI (clinical psychologist) or a clinical psychologist in training under supervision of the PI, will call the patient within 2 business days, with up to 2 contact attempts, to rule out suicide plan. This timeframe for response is seen as appropriate given 1) the extremely low likelihood that a person with an imminent suicide plan would be completing a baseline survey packet to enroll in a 2-year lifestyle intervention, and 2) the high false positive rate between the PHQ-9 suicide ideation question and an actual suicide plan. Alert values and actions for the PHQ-9 are listed in Table 7.

**Table 7. Alert Values and Actions**

Measure	Alert Value	Notify Participant	Notify PCP
PHQ-9 (Depression Questionnaire)	Total Score $\geq 15$ and $< 20$	Advise to follow up with PCP or mental health care provider	None
	Total Score $\geq 20$ but no endorsement of suicidal ideation	Advise to follow up with PCP or mental health care provider	Within 1 week
	Endorsement of suicidal ideation (regardless of total score)	Call within 2 business days to assess for suicide plan. Advise to follow up with PCP or mental health care provider.	Within 1 week

### **F3. Social risks to participants**

Personal information will be collected during the study. Group visits in the PCMH and DM arms will involve sharing personal information with other patients. A breach in data security would present a privacy risk to participants.

**Protection against risk.** Respect for confidentiality will be established as a group norm in the first session and reinforced by the group leader throughout the program. To protect confidentiality of study information and data, each participant will be assigned a unique number which will be used on all data collection forms. All electronic data capture will be stored in REDCap. Hard copy forms (e.g. original consent forms, hard copy data collection forms used by the practice), will be collected from the practice at regular intervals (via mail and in-person visits). Documents will be stored in locked secure file cabinets at KUMC. Hard copy survey forms mailed to KUMC by participants will also be stored in locked secure file cabinets.

### **F4. Economic risks to participants**

In all three arms, participants may suffer lost income or leave time from work when they attend the four in-person assessment visits, which will likely occur during regular work hours. In the FFS and PCMH arms, participants may suffer lost income or leave time as a result of in-person counseling sessions, which in the FFS arm will likely occur during regular work hours, and in the PCMH arm may occur during regular work hours or evening hours. Although we compensate for mileage to and from assessment visits, participants in the FFS and PCMH arms will be responsible for mileage costs associated with in-person counseling visits. Participants will likely be visiting their PCP more frequently than usual for study-related visits. As a result, the PCP may request to see their patients more regularly to deliver standard medical care for other co-morbid conditions (i.e. hypertension or diabetes). All standard medical care will be billed to the participant's insurance in the usual way. The participant will be responsible for any co-pays or deductibles according to their insurance coverage. In the PCMH and DM arms, participants may be billed by their cellphone companies for time spent on the phone during phone-based counseling sessions. Participants and their health insurance companies will not be charged for any visits or blood sample analysis done for this study. All information regarding economic risks are detailed in the consent form.

### **F5. Potential benefits of participation**

**F5a. Benefits to the individual.** The benefits to participants are the known benefits that weight loss and physical activity have on risk for diabetes, cardiovascular disease, arthritis, cancer, and other morbidities. Participants may also benefit from an increased ability and self-control to regulate diet and physical activity behaviors, as well as improved mental functioning, quality of life, and well-being. They will receive an evidence-based behavioral weight loss intervention, mileage reimbursement for assessment visits (not counseling visits), and debit ClinCard deposits (\$25 for survey completion at five time points, \$30 for assessment visit attendance at baseline, 6 month, and 18 month visits and \$50 at the 24 month visit).

**F5b. Benefits to the population.** Other obese adults within participants' family, social networks, and rural communities may vicariously benefit to the extent that participants share what they learn in the intervention. Participating rural practices will gain increased knowledge and effectiveness in addressing weight loss with patients, and the opportunity to collaborate with other rural practices – all of which may result in improved and expanded services available in the rural communities.

**F5c. Benefits to science and society.** The benefits to science and society include increased knowledge of the most effective model for addressing obesity in rural primary care. With 4 out of 10 rural residents currently living with obesity and a major gap in availability of obesity treatment programs, there are numerous

potential benefits for reducing chronic disease morbidity and mortality and improving quality of life in this underserved population.

### **G. Location Where the Study Will Be Performed**

This is multi-site study that will be completed in collaboration with three academic medical institutions, KUMC, the University of Nebraska Medical Center (UNMC) and the Marshfield Clinic in Wisconsin. KUMC, UNMC, and Marshfield Clinic will be responsible for coordinating study activities in practices affiliated with their institution (see Section I). Across all arms, personnel at the primary care practices will collect informed consent and conduct assessment visits. Across all arms, self-reported questionnaires will be collected outside of the in-person assessment visits, via online forms in REDCap or by mail for those patients without internet access. The location of counseling sessions will vary by arm: **FFS** participants will receive counseling sessions at their primary care practice. **PCMH** participants will receive counseling sessions from primary care clinic personnel, in-person at the primary care practice for the first four months and subsequently via group conference call. **DM** participants will receive counseling sessions via group conference calls conducted by KUMC personnel. *Participant electronic research records* will be stored on the secure REDCap database, developed and overseen by KUMC Medical Informatics. Hard copy forms will be stored long-term in a secure locked file cabinet at KUMC.

### **H. Collaboration**

KUMC will serve as the IRB of record for UNMC and Marshfield Clinic (see Section I).

### **I. Single IRB Review for a Multi-Site Study**

#### **I1. IRB of record**

All primary care practices, with the exception of 3 or 4 possible clinics from the VA Nebraska Western Iowa Health Care System (overseen by UNMC site PI), will be approved under the KUMC IRB. UNMC and Marshfield Clinic have an IRB reciprocity agreement established through the Clinical Data Research Network (PI [name]). The VA Nebraska Western Iowa Health Care System IRB application will be overseen by UNMC site PI, [name].

#### **I2. Study activities**

Centralized mail and phone-based patient recruitment and screening will occur at KUMC (see Section III). Provider trainings will be delivered both centrally and locally within the practices with collaboration and uniformity across all three institutions. Tracking of provider training completion will be managed by KUMC study personnel. Patient consent, in-person assessment visits, and FFS and PCMH counseling visits will occur within the primary care practices; these procedures will be the same across practices affiliated with KUMC, UNMC, and Marshfield Clinic. Some data collection visits may be conducted at a patient's home, or another location convenient for the patient, if they are unable to come to the primary care practice for the visit. Counseling visits for the DM arm will be conducted by KUMC study personnel for all 12 practices randomized to this arm. KUMC study personnel will also handle (for all 36 practices and 1440 patients) centralized distribution of self-report questionnaires (on-line and by mail) and related data entry, tracking of patient recruitment and retention rates, retention phone calls to patients who miss assessment visits and have not been reached by the practice, and reporting requirements for KUMC IRB and PCORI.

#### **I3. Site evaluation**

Capacity at the *institutional level* has been vetted during the grant application and review process. KUMC, UNMC, and Marshfield Clinic have ample rural primary care practice affiliations. The site investigators are

experienced in conducting clinical trials in the area of obesity and diabetes control, particularly in the rural setting, and have achieved 85-90% patient retention rates. Capacity at the *local primary care practice level* will be ascertained through multiple phone calls and in-person visits made by a group of study personnel consisting of a study physician, PI or other non-physician investigator, and a Practice Coordinator staff member. Numerous conversations with PCPs and practice staff are anticipated regarding the study requirements and activities. All practices will be required to identify a PCP champion and Practice Liaison (primary point of contact) and must be able to develop a patient registry of approximately 300-400 patients with a BMI  $\geq 30$  kg/m^2. Based on obesity prevalence rates in rural Midwest, even the smallest practices (~2000 patients) are expected to have sufficient patient numbers. Capacity will depend largely upon ability to integrate assessment visits and counseling visits into staff workloads and practice workflow. After fully vetting capacity and interest, the PCP champion and Practice Liaison will be required to commit by signing an KUMC Research Institute approved RE-POWER Practice Agreement form detailing the requirements and expectations for study participation.

#### **14. IRB-approved protocols**

All sites will use the same recruitment materials and IRB-approved protocol and consent form (consent form varying by arm). All practice staff who serve as research personnel will complete HSC training and training in protocols for collecting patient consent, conducting assessment visits, and conducting counseling visits (FFS and PCMH only). As a pragmatic trial, we will not strictly monitor adherence to counseling session guidelines but rather will offer training and support for the FFS and PCMH arms that is consistent with real-world models of care. As such, by design we are retaining the inherent differences in quality control and training in behavioral obesity treatment across the three arms, with the greatest level of training and quality control in the DM arm. In contrast, adherence to protocols for consenting patients and collecting data will be closely monitored. Initial training in study protocols will occur in-person during a central training at the start (see I5 below). Consenting protocols and assessment protocols will be demonstrated and practiced. Ongoing training will occur in-person during routine visits made by the Practice Coordinator, as well as through use webinars, and a written Standard Operating Procedures manual provided to each practice. The Practice Liaison at each practice will be trained to help ensure that only HSC-approved study materials are used and that the HSC protocol is followed. Practice Coordinators will oversee adherence to the protocols at the clinics by working closely with the Practice Liaisons. The Practice Coordinator will meet regularly with the Practice Liaison by phone and email and will visit the practice in-person at a minimum twice per year with more visits as needed.

#### **15. Communication**

[figure not shown]
The study team includes investigators and staff from the three institutions (KUMC, UNMC, and Marshfield Clinic) and personnel from the 36 local primary care practices (20 practices through KUMC, 6 through UNMC, and 10 through Marshfield Clinic); See Organizational Chart. The PI will meet with her research staff at least weekly to oversee all aspects of the study. The PI will meet with all co-investigators at KUMC, UNMC, and Marshfield Clinic at least monthly via conference call or Skype to discuss project updates, questions and concerns, and progress with recruitment and retention for each clinic to ensure consistency in study implementation across the three institutions.

Communication between primary care clinics and the affiliated institution will occur primarily between the Practice Coordinator (central study personnel) and Practice Liaison (clinic study personnel). The KUMC study team includes a full-time Lead Practice Coordinator responsible for coordinating implementation of the study protocols across the primary care clinics. In addition to working closely with the other Practice Coordinators (staff from KUMC and one each at UNMC and Marshfield Clinic), she will serve as the primary contact for approximately 12 clinics affiliated with KUMC. The Lead Practice

Coordinator will manage delivery of all provider trainings and regulatory compliance across all 36 clinics and facilitate communication with practices related to the study activities they oversee.

Prior to launching each cohort, we will hold a central day-long training for practices enrolling patients for that cohort. The PCP and Practice Liaison will be asked to attend, as well as any other clinic staff who may conduct visits or counseling sessions. It is expected that not all clinic staff involved in the study will attend the central training, especially given the likelihood of staff turn-over during the course of the study. Therefore, all training material covered during the central trainings will also be made available through podcasts, and on-line materials. The central training will serve to enhance working relationships, build enthusiasm for the larger scope and mission of the project, and facilitate effective communication at the start that will be maintained throughout the study period. The central training will cover human subjects protection (delivered by study personnel with prior approval from IRB), use of REDCap, study protocols, and obesity treatment guidelines and counseling skills.

### Organizational Chart

### 16. Protocol compliance & Serious Adverse Events

The Practice Liaison or other practice staff will be responsible for completing the Serious Adverse Event Record Form in REDCap to the extent possible for all serious events that become known to the practice. The Practice Coordinators, overseen by site PIs, will work closely with each site to routinely assess protocol compliance and reporting of SAEs in a timely fashion. Central study personnel will initiate the Serious Adverse Event Record Form for events that become known outside of patients presenting at the practice; the practice will be asked to final the form with the more complete information available to them at the site. The PI will oversee compliance to SAE reporting timeframes with close monitoring of automated reports of Serious Adverse Event Record Forms in REDCap.

## **J. Personnel Who Will Conduct the Study**

### **J1. Titles of those who will be present during study procedures**

- a. Informed Consent: Practice Liaison, Care Coordinator (i.e. nurse, RD, or behavioral counselor) or another clinic-employed health professional under PCP supervision
- b. Assessment Visits: Practice Liaison, Care Coordinator or another clinic-employed health professional under PCP supervision
- c. Counseling Visits:  
**FFS** arm: PCP, Care Coordinator, or another clinic-employed health professional under PCP supervision  
**PCMH** arm: Care Coordinator (nurse, RD, or behavioral counselor)  
**DM** arm: KUMC obesity treatment specialists (RD, psychologist, or other trained obesity treatment specialist)

### **J2. Primary responsibility for study activities**

- a. Determining eligibility: KUMC Recruitment Coordinator, PI, and primary care clinic study personnel
- b. Obtaining informed consent: Practice Liaison, Care Coordinator or another clinic-employed health professional
- c. Providing on-going information to the study sponsor and the IRB: Lead Practice Coordinator and PI
- d. Maintaining participants' research records: Practice Liaison, Care Coordinator, and KUMC research team
- e. Taking anthropomorphic measures: Care Coordinator or another clinic-employed health professional
- f. Collecting laboratory specimens: Nurse or phlebotomist at or serving primary care practice.
- g. Performing counseling interventions: PCP, Care Coordinator or another clinic-employed health professional under PCP supervision; KUMC study personnel (obesity treatment specialists).
- h. Completing patient-report questionnaires: participants will complete questionnaires via email or mail distributed by KUMC study personnel
- i. Entering study data into REDCap: Practice Liaison, Care Coordinator or other clinic-employed health professional; KUMC research team
- j. Managing study database: the study database will be managed by the KUMC Medical Informatics, the KUMC Department of Biostatistics (Biostatistician: [name]; Data Analyst: [name]), and study personnel under the PI.

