## B. Study Type and Design

The study is a cluster randomized pragmatic trial comparing **PCMH (in clinic group visits)** and **DM (phone group visits)** to **FFS (in clinic individual visits)** in 36 rural primary care practices throughout the rural Midwestern U.S (Figure 2). The FFS condition will include PCP delivered (or supervised) obesity counseling sessions following the session schedule reimbursed by the Medicare Intensive Behavioral Therapy provision. The PCMH and DM arms will include a common group-based evidence-based comprehensive lifestyle intervention, but the delivery mechanism will differ. In the PCMH arm, the intervention will be delivered by personnel within the office practice using in-person group office visits, option to switch to group phone conference calls, plus individual phone contacts and email/text support as deemed feasible and appropriate by the practice. PCMH practices will receive intensive and on-going training to build their capacity for delivering this care. In the DM arm, the intervention will be centrally delivered by obesity treatment specialists using group visits via conference calls, and patient progress will be routinely communicated back to the PCPs. The primary outcome is weight loss at 24 months, and secondary endpoints include other patient-centered outcomes. See study flow for more details (Figure 4; page 27)

Figure 2. Study Design

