## **C2. Blinding**

Randomization happens at the practice level. Blinding practice staff or study staff is not feasible during a behavioral trial. However, throughout the study investigators and study personnel will communicate and

demonstrate equipoise (genuine uncertainty) with practice staff and patients about the relative benefit of the three arms.

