**Table 2. Practice Personnel Roles**

Personnel	Role
Primary Care Provider (MD, DO, PA, or NP)	
 
• Study Champion
 
• Provides counseling in the FFS arm or supervises health professional
 
• Provides feedback and encouragement in PCMH and DM arms
 

Practice Liaison (office manager, nurse, etc)	
 
• Point of contact at practice
 
• Communicates regularly with study team at KUMC
 
• Schedules participants, ensures forms are completed, and protocols are being adhered to
 

Care Coordinator/Counselor (nurse, dietitian, or behavioral counselor)	
 
• Provides counseling in the PCMH arm
 
• Oversees and organizes enrolled participants' care
 
• Can be same person as Practice Liaison
 

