## **E2e. Outcome measures**

Outcome measures have been selected with input from our Patient Advisory Board and are supported by the literature. See Table 5 for the list of measures and estimated time to complete. The goal will be to complete the assessment visits within a -7 days/+21 day window of the target date. We will allow for a 3 month window for 6 and 18 month visits if an assessment visit appointment needs to be rescheduled and a 4 month window for the 24 month visit if an assessment visit appointment needs to be rescheduled. Chart review may be used to capture medications and number of clinic visits as well as missing weight data.

**Anthropomorphic measures.** Weight, and blood pressure will be directly measured and recorded at baseline, 6, 18, and 24 months during in-clinic assessment visits. Height will be measured at baseline only. These measures will be collected by clinic staff. Participants will be weighed in light clothing (shorts and t-shirt) in a fasting state using a calibrated digital scale accurate to 0.1 kg. Height will be measured with a stadiometer to calculate BMI. Blood pressure will be measured by clinic staff after the patient rests in a seated position for 5 minutes. Two measurements will be taken and recorded. If either the systolic or diastolic measurements are greater than 5mm Hg apart, a third measurement will be taken after a one-minute break. Estimated time for in-person assessment visit procedures is 15-20 minutes. If a patient is unable to come to the clinic for the data collection visit, an in-home visit or a visit at another location convenient for the patient, may be conducted.

**Fasting glucose and lipids.** A clinic phlebotomist or nurse will collect blood samples required for analysis of fasting glucose and lipids, to include LDL, HDL, triglycerides, and total cholesterol. Laboratory results

will be sent to the PCP per the laboratory and practice's standard operating procedures. The practice will in turn provide the results to KUMC study personnel (see section E1 for specifics).

**Questionnaires.** Self-report questionnaires will be administered via on-line REDCap surveys sent by email or by hard copy surveys sent via regular mail, depending on patient preference. Patients will be asked to complete questionnaires at all five time points (baseline, 6, 12, 18, and 24 month visits). Patients must complete the baseline questionnaires prior to enrolling in the trial (see section C1).

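### The unblinded counsellor may weigh their own participants in PCMH, and possibly in FFS, but the listed roles exclude this in DM, so recording of the primary outcome could differ by arm

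*Combined protocol and SAP*

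**What the plan says.** Section II.B sets the endpoint: "The primary outcome is weight loss at 24 months". Section II.C2 states: "Blinding practice staff or study staff is not feasible during a behavioral trial". It commits staff to conveying equipoise, but does not consider a masked or separate weigher.

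On who measures weight:

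- Section II.G: "Across all arms, personnel at the primary care practices will collect informed consent and conduct assessment visits".
- Section II.E2e, on weight, height and blood pressure: "These measures will be collected by clinic staff".
- Section II.J2(e): "Taking anthropomorphic measures: Care Coordinator or another clinic-employed health professional".
- Section II.J1(b), on assessment visits: "Practice Liaison, Care Coordinator or another clinic-employed health professional under PCP supervision".
- Section II.J2(i) lets the same practice roles, as well as the KUMC team, enter data into REDCap.

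On who counsels:

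- PCMH: the J1(c) entry reads "arm: Care Coordinator (nurse, RD, or behavioral counselor" (closing bracket omitted here). Table 2 adds, for this counsellor: "Can be same person as Practice Liaison".
- FFS: the PCP, the Care Coordinator or another supervised clinic employee (Table 1, J1(c)).
- DM: remote specialists employed at KUMC, for all 12 practices (II.E2c, II.I2, J1(c)).

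The plan has safeguards for the measurement. E2e requires a calibrated digital scale accurate to 0.1 kg, light clothing and a fasting state. Section II.I4 provides training, a procedures manual and close monitoring of data collection. Section IV.E1 adds certification and yearly observation of practice staff, and IV.E2 adds weekly logic checks on weight. Section IV.E3 plans no third-party data monitoring.

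**The concern.** In PCMH, and in FFS where the PCP does not counsel, the person whose work the trial evaluates may read the scale and enter the result. In DM the listed roles do not allow that. The opportunity for the weigher to have a personal stake in the reading is therefore tied to the randomised arm.

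Relevant behaviours include re-weighing after a disappointing reading, generous rounding, and laxer application of the clothing or fasting rules as follow-up goes on. An arm-specific shift of this kind cannot be told apart from a treatment effect in the mixed model of Section II.C1. The documents do not provide for recording who took each weight, so its influence could not be examined afterwards either. The affected variable is the endpoint for both primary contrasts and for the secondary DM–PCMH contrast.

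**Working it through.** **Step 1. Set the roles side by side.**

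| Arm | Counsellor | Listed weigher (J2(e)) | Can they be the same person? |
|---|---|---|---|
| PCMH | Care Coordinator | Care Coordinator or other clinic employee | Yes; the first-named weigher is the counsellor |
| FFS | PCP, Care Coordinator or other clinic employee | As above | Possible, depending on who counsels |
| DM | KUMC remote specialist | As above | Not under J2(e) and II.G |

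No section bars a counsellor from weighing their own participants. The DM entry is an inference from J2(e) and II.G: E2e permits home or off-site visits without saying who weighs there.

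**Step 2. Ask which habits matter.** Section II.C1 models weight change, and clinic staff also take the baseline weight. A constant habit largely cancels in the change from baseline. Only behaviour that differs between baseline and follow-up biases an arm's mean.

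**Step 3. Identify the exposed contrasts.** If a share p of an arm's follow-up weights is counsellor-taken, and each is shifted by d kg relative to baseline practice, the arm mean shifts by p × d. The net bias in a contrast is the difference between the two arms' values of p × d.

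- DM–PCMH and DM–FFS: the DM term for counsellor weighing is zero, so nothing offsets the other arm. Extra recorded loss in PCMH or FFS works against DM.
- PCMH–FFS: both terms can be non-zero and may partly cancel.

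**Step 4. Reproduce the plan's power figure.** Inputs from Section II.C3: 12 practices of 40 per arm, SD 8 kg, ICC 0.05, type I error 0.025 per primary comparison, target 2.75 kg. Sidedness is not stated.

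- Design effect = 1 + (40 − 1) × 0.05 = 2.95.
- Effective n per arm = 480 / 2.95 = 162.7.
- SE of the difference = 8 × √(2 / 162.7) = 0.887 kg.
- Two-sided power = Φ(2.75 / 0.887 − 2.2414) = 80.5%, matching the stated 80%. One-sided 0.025 would give 87.3%, so two-sided is used below.

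**Step 5. Illustrate the consequence of a net shift s.** The values of s are assumptions.

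- Actual two-sided error under no true effect = P(Z > 2.2414 − s/0.887) + P(Z < −2.2414 − s/0.887).
- Power if the true effect is 2.75 kg and the shift works against it = Φ((2.75 − s)/0.887 − 2.2414).

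| Net shift s (assumed) | Share of 2.75 kg | Actual error (nominal 2.5%) | Power, shift against |
|---|---|---|---|
| 0.25 kg | 9% | 3.1% | 71.8% |
| 0.5 kg | 18% | 4.9% | 61.6% |
| 1.0 kg | 36% | 13.3% | 39.4% |

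At 80% retention (32 per practice), the design effect is 1 + 31 × 0.05 = 2.55, the effective n is 384 / 2.55 = 150.6 and the SE is 0.922 kg. The errors become 3.0%, 4.7% and 12.4%.

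**Step 6. Allow for dilution.** These are net, arm-level shifts. If counsellors took half of one arm's follow-up weights and there were no offset in the other arm, a 0.5 kg arm shift would need 0.5 / 0.5 = 1.0 kg on each counsellor-taken weight.

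**The case against.** The strongest reply is that weight on a calibrated scale is a fairly objective endpoint and is well protected here. A clothing allowance would breach E2e. Staff are trained, certified and observed, suspect values are flagged, and weight is checked weekly. The procedures manual is not among the documents and may contain finer rules. J2(e) also lets another clinic employee weigh, so overlap is permitted rather than shown. Use of clinic staff is an open pragmatic choice, and C2 acknowledges the lack of blinding.

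Most of this stands, and it limits the room for bias. It does not remove the point: none of the documented safeguards separates weigher from counsellor. A logic check aimed at out-of-range values would not notice half a kilogram, and yearly observation sees few visits.

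A reader might infer four stronger things that the documents do not support:

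- That the weights are biased. The documents show an opportunity, not its use.
- That the error rates above are the trial's error rates. The shifts are assumed, and Section II.C3 gives the 0.025 level only to the first two aims, so the error illustration does not apply to DM–PCMH.
- That DM weights are masked. DM clinic staff are unblinded too; they lack only the counsellor's own stake.
- That counsellor-taken weights should be dropped. This would select on a post-randomisation feature, remove data only from PCMH and FFS, and depart from the intent-to-treat analysis in Section II.C1.

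**Conclusion.** The concern holds as a possible arm-related recording bias in the primary endpoint. The documents allow the unblinded counsellor to take and enter their own participants' weights in PCMH, possibly in FFS, and not within the listed roles in DM. It matters only for behaviour that changes after baseline. DM–FFS (primary) and DM–PCMH (secondary) are most exposed; PCMH–FFS is less certain.

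Its size is unknown. The error range of 3.1% to 13.3% is illustrative and rests on three assumptions: a net arm-level shift of 0.25 to 1.0 kg, the plan's own SD and ICC, and a two-sided 0.025 test. The sample size and stated power need no change. The point merits a correction because the protection is cheap, not because the results are shown to be unsound.

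**What to change.** 1. In J2(e) and E2e, state that follow-up study weights are taken and entered, wherever the practice has one available, by a clinic employee who has not counselled that participant, with no earlier study weights shown on the entry form. Where nobody else is available, the weight is still taken.
2. Add a REDCap field for the weigher's role, recover it where possible for completed visits, and tabulate it by arm and visit.
3. Keep every weight in the primary intent-to-treat analysis. Add a sensitivity analysis that shifts counsellor-taken follow-up weights by a range of assumed amounts, for example 0.25 to 1.0 kg, instead of excluding them.

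The cost is one scheduling rule using staff whom J1 and J2 already allow, one data field and one extra analysis, with no new staff or visits. Scheduling becomes slightly less flexible in very small practices.

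The rule can affect only visits not yet done. On the Section II.E5 timeline, cohort 3 starts recruiting in September 2016; 9 months of FFS enrolment and 24 months of follow-up run to about June 2019. A Table 5 footnote shows that the text was revised after 18-month visits began. If most weights have already been taken, items 2 and 3 carry the benefit.
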